#### 9.2.2 Outcomes of interest

# Thrombotic thrombocytopenia syndrome (TTS) case definition (general population)[6]

The precise definition of thrombotic thrombocytopenia syndrome (TTS) is challenging. We will start with a broad definition. Thrombocytopenia defined either by diagnosis or platelets recording within 7 days of Thromboembolism dg. These definitions and the planned sensitivity will be iteratively adapted after reviewing available data. For example, we may rather than use

a fixed platelet count threshold use a drop of platelet count below a certain threshold or change the time interval between TE and TCP.

Sensitivity Definitions include:

a.

Operationally, see **Figure 1**, a patient will have a new\* diagnostic code for thrombocytopenia (TCP) OR a new\* platelet count , see Diagram:

- a. Within 7 days from thromboembolism event, i.e., from 7 days prior to and up to 7 days after index event (based on observation that spontaneously reported TTS cases are largely based on diagnoses during hospitalisation)
- b. (sensitivity period) within \_7/+42 days from thromboembolism event (reflecting on strengthening the association between TE and TCP events)

\*'new' TCP is defined by excluding any prior TCP diagnosis during prior 12 months OR platelet count 10 to less than 100 (150 for sensitivity) x10^9/L during prior 3 months.

[figure not shown]

Figure 1: Analysis approach & associated time periods

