The matched case-control study will be conducted to determine the likelihood of those presenting with thrombotic thrombocytopenia (TTS) events within a risk window of 28 days of receiving COVID 19 vaccination. Patient who fulfils the definition of thrombotic thrombocytopenia based on a distribution of TTS spontaneously reported cases for COVID-19 vaccine AstraZeneca (sensitivity windows of 42 days as risk window for many immune-mediated vaccine safety events and as per EMA recommendation. We will conduct exploratory analyses on the dataset with the definitive analysis conducted on the national data held in the NHS Digital TRE, to identify people who presented with thrombotic, and thrombocytopenia events over a period (02 December 2020 to end of data availability, estimated mid May 2021) following COVID-19 vaccination. Electronic records of cases will be checked for any previous recorded history of conditions consisting of TTS; several wash-out periods will be considered including prior 90 days or prior for 12 months prior to the date of the index episode. Those without a previous record will be deemed to have experienced an incident diagnosis of a TTS on that date. Each incident case will be matched by date of TTS event,

Diagnosis dates of the cases will be considered the index dates for the controls. Records of both cases and controls will then be checked for the 28 days (sensitivity period of 42 days) before the index date for a previous ChAdOx1 and BNT162b2 or other COVID-19 vaccination.

For the self-controlled case series (SCCS), only individuals with a TTS event recorded during the defined study time are included in the analysis. Event and exposure history will be obtained from the linked dataset; events primarily extracted from hospital data. We will control for potential delaying of vaccination by the occurrence of an event by using the pre-vaccination risk period -7 to -1 days. Furthermore, since venous thromboembolism (VTE) is a likely indication for administration of a vitamin K antagonist (warfarin) or direct oral anticoagulants (DOAC), SCCS models with both vaccination and anticoagulation as exposures are potentially subject to event-dependent exposures, including recent infection. In this case we will perform a subgroup analysis of those with historical anticoagulation (defined by a prescription for

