## 9.6 Data analysis

## 9.6.1 Statistical Methods – General Aspects

A detailed Statistical Analysis Plan (SAP) will be developed for this analysis. The SAP may modify the plans outlined in the protocol; any major modifications of primary endpoint definitions or their analyses would be reflected in a protocol amendment. For all study designs, P-values will be quoted to two decimal places, unless they are less than 0.001 (whereby the p-value will be given as <0.001) or between <0.005 and >0.001, in which case they will be stated to three decimal places. Parameter estimates will be reported with 95% confidence intervals. All statistical tests are two sided and with a 5% significance level. All statistical analyses will use the R statistical software.

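### Section 9.2.2 provides for changing the TTS definition after data review, and the visible text requires neither masking to vaccination nor a lock before the exposure-outcome analysis

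*Protocol*

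**What the plan says.** Protocol section 9.2.2 calls a precise TTS definition challenging and starts from a broad one: "Thrombocytopenia defined either by diagnosis or platelets recording within 7 days of Thromboembolism dg". It then states: "These definitions and the planned sensitivity will be iteratively adapted after reviewing available data". Two examples of change follow, the platelet rule and the interval between thromboembolism (TE) and thrombocytopenia (TCP): "a fixed platelet count threshold use a drop of platelet count below a certain threshold or change the time interval between TE and TCP".

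Several options are visible:

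- **TE-TCP interval.** The main window is "Within 7 days from thromboembolism event, i.e., from 7 days prior to and up to 7 days after index event". A sensitivity window runs to +42 days (section 9.2.2).
- **Platelet threshold.** The footnote that defines new thrombocytopenia gives "platelet count 10 to less than 100 (150 for sensitivity". The threshold for the case itself is not legible in the public text.
- **Wash-out for an incident case.** Section 9.1 says "several wash-out periods will be considered including prior 90 days or prior for 12 months".

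Two statements bear on control of the changes. Section 9.6.1 says that the SAP may modify the protocol's plans and that "any major modifications of primary endpoint definitions or their analyses would be reflected in a protocol amendment". Section 9.1 places exploratory analyses on one dataset (name removed), "with the definitive analysis conducted on the national data held in the NHS Digital TRE".

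Section 9.6.1 also fixes two-sided tests at the 5% level and 95% confidence intervals.

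**The concern.** TTS is the only outcome in the objective (section 8), and section 9.13 names the case definition as the main limitation. Some flexibility is reasonable for a new syndrome. The difficulty is that the protocol provides for repeated change after data review without saying what the reviewers may see or when the changes stop.

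The data are retrospective and linked, and they include vaccination (abstract; section 9.3). Unless exposure is masked, whoever compares candidate definitions can also see how each one relates to vaccination. A definition settled that way is partly selected on the result. The reported p-value and confidence interval would then describe the chosen version as if it had been the only candidate.

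This is a post-authorisation safety study of a named product. A finding in either direction would be open to challenge if the record could not show that the outcome was fixed without knowledge of exposure.

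**Working it through.** **Step 1. Do the stated safeguards close the gap?**

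| Provision | What it does | What it leaves open |
|---|---|---|
| Section 9.2.2, adaptation | Commits to iterative change; names platelet rule and interval | Masking, lock, end of iteration |
| Section 9.6.1, amendment | Makes major changes traceable | Timing, masking, meaning of major |
| Section 9.1, two datasets | Separates exploratory from definitive work | Whether the definition is frozen in between |
| Appendix B, checklist | Answers No on analytic control of outcome misclassification and on independent review of results | Offers no further safeguard |

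None of these requires the definition to be settled without knowledge of vaccination.

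**Step 2. How many definitions are in play?** The protocol gives no figure for this, so there is none to reproduce. The cells of the section 9.4 study-size table are blank in the public text.

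- Platelet rule (2) × interval (2) = 4 definitions. These are the two levers that section 9.2.2 names. Taking two platelet options is an assumption, because 100 and 150 are stated only for the footnote on new thrombocytopenia.
- With two wash-outs (section 9.1): 4 × 2 = 8. Section 9.1 lists the wash-outs in advance, and they are not among the changes that section 9.2.2 names. Eight is therefore the wider count.

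**Step 3. Bound if the definitions were independent.** The chance that at least one of k tests reaches p<0.05 with no association is 1 − 0.95^k:

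- k = 1: 0.050
- k = 4: 1 − 0.95^4 = 0.186 (rounded up from 0.1855)
- k = 8: 1 − 0.95^8 = 0.337

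The real definitions share cases, so the true values are lower.

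**Step 4. Simulation with overlapping definitions.** All inputs are assumptions: a Poisson number of cases under the loosest definition, mean 150; 20% expected exposed; each stricter criterion met independently by a fixed share of cases. For definition d with N_d cases, of whom E_d are exposed,

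z_d = (E_d − 0.2 N_d) / √(N_d × 0.2 × 0.8),

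significant if |z_d| > 1.96. This stands in for the matched analysis, with exposure among controls treated as known.

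| Definitions | Share meeting each stricter criterion | Some version p<0.05, no association |
|---|---|---|
| 1 (loosest) | – | 5% |
| 4 | 80%, 80% | 10% |
| 4 | 50%, 50% | 13% |
| 8 | 50%, 50%, 80% | 18% |

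The null figure changes little with the case count: for eight definitions it is about 17% at 60 cases and 18-20% at 400.

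**Step 5. Cross-check by another method.** With equally correlated z-statistics (correlation 0.9, 0.8, 0.5, assumed), the chance of at least one p<0.05 is 0.096, 0.114, 0.157 for four definitions and 0.120, 0.158, 0.249 for eight. The simulated values lie within these ranges.

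**Step 6. The opposite direction.** With a true odds ratio of 2, the exposed odds rise from 0.2/0.8 = 0.25 to 0.50, so the exposed share is 0.50/1.50 = 33%. At 150 cases, at least one non-significant version exists in 16% of studies (four definitions, 80%/80%) and in 66% (eight definitions, 50%/50%/80%). Much of this is loss of cases: the strictest of the eight keeps 0.5 × 0.5 × 0.8 = 20%, or about 30 of 150, and has only about 45% power by itself. With 400 cases, the 66% falls to 22%.

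**The case against.** The strongest reply is that the protocol is silent on masking and does not rule it out. Reviewing the data may mean no more than checking which codes and platelet counts are available, which fits the remarks on an unsettled definition and multiple codes (sections 9.2.2 and 9.13). A detailed SAP is promised and could set the masking and the lock. Parts of section 9.2.2, including the case platelet threshold, a sensitivity item and Figure 1, are not visible.

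Much of this stands, and it limits what can be said. A reader might infer any of the following, and the documents support none of them:

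- **That the outcome will be tuned on its association with vaccination, or that masking is excluded.** The text permits exposure-informed choice; it does not state it.
- **That the 5% level and the confidence intervals already fail.** They fail only if the version is chosen with knowledge of its result.
- **That the definitive analysis reuses the exploratory patients.** Section 9.2.1 mentions RCGP RSC and section 9.3 describes a collection from all GP practices in England, so overlap is plausible. The name of the exploratory dataset is removed, however, so overlap is an inference of unknown extent.
- **That a real effect could usually be hidden.** The 16% to 66% range depends on the assumed case count and criteria. The simulated loosest definition is also not the protocol's starting one, which uses the 7-day interval.

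The reply does not remove the point. The protocol does more than leave the definition to the SAP: it provides for data-driven change of its only outcome and attaches no masking or timing condition. An amendment records that a change was made, but does not show that it was made without sight of exposure.

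**Conclusion.** The point holds as a statement of what the protocol permits. Section 9.2.2 commits to changing the outcome definition after data review, and no visible provision requires masking to vaccination or a lock before the exposure-outcome analysis.

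If a version were selected on its result, the chance of a nominally significant finding under no association would rise from 5% to about 10-14% with four definitions and 18% with eight. These figures are illustrative. They rest on assumed values for the case count, the exposed share and the proportion of cases meeting each criterion, and on two platelet options that are partly inferred. The need for a lock does not depend on them. With one definition locked before any look at exposure, the level stays at 5%.

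**What to change.** In section 9.2.2, state that:

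1. the TTS definition may be adapted only on case counts, code and platelet availability, and clinical profile, with vaccination status, date and brand masked;
2. the primary definition is locked and dated, in the SAP or a protocol amendment, before any exposure-outcome analysis of the national data;
3. the broad starting definition and all later variants are reported alongside it as sensitivity analyses.

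The lock should be tied to the analysis, not to data linkage, because the abstract and section 9.3 describe data that are linked or linkable within the research environment.

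Optionally, if the exploratory data prove to overlap the national data and the practices can be identified, repeat the primary odds ratio without those practices.

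The cost is masking the exposure fields during definition work and less freedom to revise the definition afterwards. No sample size or power figure changes.

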#### 9.3 Data sources

[figure not shown]
This study will employ linked England's national databases for data on

The datasets use unique identifiers allowing linkage across the datasets and avoidance of duplicates. We will assemble the required datasets for the analysis in the final analysis with the national data held in the final analysis with the national data held in the

provides access to data. Through this service it is possible to request access to several secondary data assets collected as part of routine care and commissioning activities in the linkable to the primary care data in linkable in their own linkable in their own linkable in their own linkable through linkable t

- GPES data for pandemic planning and research (GDPPR): central collection of GP patient data for COVID-19 purposes (fortnightly collection All GP practices in England).
   only, the rest of these data will also be linked to data.
- includes 2 associated datasets including COVID-19 Vaccination Status and COVID-19 Adverse Reaction.
- Hospital Episode Statistics (HES): this is the transformed data, initially part of the Commissioning Data Set (CDS), covering patients attending accident and emergency units, admitted for treatment, or attending outpatient clinics at hospitals in England. Statistical controls have been applied to the HES products. (Time lag 8-12 weeks).
- COVID-19 Second Generation Surveillance System (SGSS) Demographic and diagnostic information from laboratory test reports for patients tested for COVID-19 in England only. It currently includes the first positive results from pillar 1 (swab testing in and hospital labs and pillar 2 (swab testing for the wider population) (Time lag less than 1 week).
- Covid-19 UK Non-hospital Antigen Testing Results (Pillar 2) data includes a range of COVID19 test results, including

[figure not shown]
   This is broadly like SGSS, but only covers Pillar 2 data, however, contains the full result set i.e., all positive, negative, and null results.
- COVID-19 Hospitalization in England Surveillance System (COVID-19 SARI-Watch/CHESS): Epidemiological data on COVID-19 infection in persons requiring hospitalization in Intensive Care Units (ICU) or High Dependency Units (HDU). It records all demographic, risk factor, treatment and outcome information for patients admitted to hospital with a confirmed COVID-19 diagnosis (Time lag less than 1 week).

## 9.4 Study size

To be further developed using feasibility counts

In Interim, Table 1 shows the probability that the upper bound of the 95% confidence interval (CI) around the observed relative risk will be below 1.5, 2.0, 2.5, and 3.0 for various study sizes and TTS rates. These calculations assume a 1-to-1 ratio of vaccinated to comparator person-time and that the true IRR between those vaccinated and those unvaccinated is 1.0.

Estimated background	People vaccinated	Upper confidence limit of IRR					
rate per 100,000 PY		1.5	2.0	2.5	3.0		
2							
		>>					
Ī							

days

Note: calculations assume a true IRR of 1.0 and a ratio of 1 to 1 exposed to unexposed person-years. Calculations also assume that each person contributes to 84 days (42-day risk interval x 2 doses). Calculations follow the method of IRR, incidence rate ratio; PY, person-years; RR, risk ratio. [13]

## 9.5 Data management

All statistical analyses will use the R statistical software, use of the SCCS library version 1.2 will be made

## 9.6 Data analysis

## 9.6.1 Statistical Methods – General Aspects

A detailed Statistical Analysis Plan (SAP) will be developed for this analysis. The SAP may modify the plans outlined in the protocol; any major modifications of primary endpoint definitions or their analyses would be reflected in a protocol amendment. For all study designs, P-values will be quoted to two decimal places, unless they are less than 0.001 (whereby the p-value will be given as <0.001) or between <0.005 and >0.001, in which case they will be stated to three decimal places. Parameter estimates will be reported with 95% confidence intervals. All statistical tests are two sided and with a 5% significance level. All statistical analyses will use the R statistical software.

## 9.6.2 Cohort design

Crude IRs and 95% CIs of each of the TTS will be estimated for and comparator cohort. These analyses will primarily combine person-time at risk after dose 1 and dose 2 (if it was received). Exploratory analyses will report the IRs by specific dose, i.e. dose 1, dose 2. As TTS is a relatively new concept, the validity of risk windows, will be evaluated through cumulative incidence estimated using 1 – Kaplan-Meier survival curves starting at the index date.

For comparative design using (potentially, subject of decision when outputting cohort description) retrospective cohort analysis, we propose using time-to-event analyses. Cox regression models with robust estimation of the variance will be used to estimate crude and adjusted hazards ratios and 95% CIs. Using Cox regression models allows the flexibility to

potentially adjust for time-dependant covariates, such as intercurrent COVID-19 infection. Adjustment for confounding will occur using PS, either through PS matching or by analytic methods involving stratification or weighting, which will be specified in the SAP. If important covariates remain imbalanced after final selection of the cohorts for comparative analyses, additional approaches for confounding adjustment will be considered, including double-robust methods (ie, including the covariate in the outcome model as a separate term) or through analyses that restrict the population to subjects with more similar baseline characteristics (eg, subjects without substantial comorbidity).

## 9.6.3 Self-controlled case series (SCCS)

For comparative analysis using the SCCS approach, conditional Poisson regression will be used to estimate IRRs and 95% CIs. Estimates of relative incidence (RI), in all risk intervals and by age groups will be reported.

Exploratory analyses may stratify by dose, depending on available sample size. Time-invariant confounders will be inherently adjusted for using the SCCS design; however, time-varying confounders (e.g. recent prior infection) will be included as covariates in regression models.

5]

#### 9.6.4 Matched case-control

For matched case-control analysis, the sampled risk sets will be represented matched strata, which will be included in conditional logistic regression models to estimate odds ratios (OR) for the risk of the event in the 42-day risk period.

. Confounding may to be due to time varying confounders that will be much harder to adjust for than in our case-control study. We will also have confounding due to the differential availability of the vaccines, their storage requirements and intervals between doses (initially short and applied mainly to one brand) and then lengthened. We may be able to adjust for those that are measured and complete;

as well as recognising others may be unmeasured (such as occupation). We will stratify exposure by dose as an exploratory analysis.

# 9.7 Subgroup analyses

A subgroup analysis will be conducted

Further subgroup analysis will be considered

. Further subgroup analysis will be of those

## 9.8 Sensitivity analyses

To reduce the potential for ascertainment bias, we will carry out a sensitivity analysis with a censoring date prior to the first media reports of possible

(i.e., March 07, 2021). We will consider exploring the use of different time intervals in the SCCS analysis following administration of the vaccine to define risk intervals to determine robustness of model estimates. Cases newly exposed to low weight molecular heparin (LWMH) direct oral anticoagulants (DOACs) or Warfarin in the post vaccination period, will be reported to explore if there are potentially missed cases.

## 9.9 Exploratory analyses

Artificial intelligence (AI) methods offer an alternative to conventional medical statistical approaches, through permitting potentially complex interactions between input covariates; permitting non-linear associations between inputs and risk; providing estimates of uncertainty in output classifications; in providing patient-specific estimates of risk (rather than population-based estimates); and in an improved ability to handle missing or artefactual data. AI-based approaches (enumerated below) will be compared with the conventional statistical approaches (enumerated below), using the same input data, for (i) predicting outcomes listed above and (ii) determining whether phenotypical groups may be defined using the input covariates that correspond to different risk models. This comparison will be undertaken using standard classification metrics (AUC, sensitivity-specificity, precision-recall, F1-score, etc.).

These AI-based approaches will include the major classes of models: ensemble methods (random forests, XGBoost, gradient-boosted trees), kernel methods (support vector machines), and deep learning methods (of varying architectures). Visualisation (via tSNE / UMAP algorithms) will be performed to facilitate interpretation of the outputs of the AI models. Feature selection and feature relevance will be undertaken to determine the primary risk factors learned by each of the AI models, for comparison against those risk models determined using conventional statistical methods. We emphasise that these are associations, and not causal, relationships – directly comparable to those of conventional medical statistical approaches.

# 9.10 Falsification Analysis

We will consider conducting a falsification analysis (negative controls) using a fictional date of exposure that is two months prior to receiving the first vaccine dose in order to estimate the influence of variables that are not directly associated with immunological effects of the vaccine (e.g., behaviour changes associated with the rollout programme) on our estimates.

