#### 9. RESEARCH METHODS

#### 9.1 **Study design-General Aspects**

A case control study and a self-controlled case series (SCCS) will be designed and run, with a cohort analysis being considered in addition or as an alternative primary study design, pending feasibility assessment of the follow-up time available. The observation period will generally start on 02 December 2020 (approval date of the first COVID-19 vaccine) to the TTS event date or end of data availability, estimated mid May 2021 or another censoring event. There are several considerations to take when selecting the final study design/s. Firstly, some assumptions of the SCCS could be violated: 1) the occurrence of an event of interest must not alter the probability of subsequent exposure; and 2) the occurrence of the event of interest must not censor or affect the observation period. This is because in case of TTS occurring after the first dose of vaccine, the second dose could not be administered and/or because of a possible high CONFIDENTIAL AND PROPRIETARY

fatality rate associated with TTS. Observation period will be censored at the time of fatal events. In conclusion, the case-control design is likely to be more appropriate as the main analysis and SCCS is proposed as a sensitivity analysis for the non-fatal cases using the extended method for curtailed post-event exposure.

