anticoagulation 90-days prior to the beginning of the study use versus those with no such history. We may also use this as a time varying covariate in our SCCS analysis). Another subgroup analysis will include prior exposure to COVID-19 infection. The observation period will commence 42 days before the first administration of a COVID vaccine in England, this results in the date 26th October 2020. The SCCS risk periods will be defined as days -7--1, 0-2, and 3-28 (our later analysis will extend to 42 days) where day 0 is the day of vaccination. This post vaccine period proposed is hypothesised to capture the time period within which most VTE events occur. A control period after 1st dose of 42 days will be considered. Given that most vaccinated in the UK were given the two-vaccine disease with about 3-month (90 days) time interval, we will check, but will not expect a high probability of overlapping of risk period after 2nd dose.

For the retrospective cohort design, the incidence of TTS after receiving COVID-19 vaccine will be estimated and we will compare this incidence with that occurring in an unvaccinated comparator group. A cohort of concurrent matched subjects will be selected. The comparison cohort will comprise subjects who have not yet received any COVID-19 vaccine.

[figure not shown]

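### The fictional-date falsification test makes exposure depend on surviving TTS and being vaccinated afterwards, so in the case-control design a result near 1 can hide upward bias

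*Protocol*

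**What the plan says.** Section 9.10 says that the sponsor will consider a negative-control analysis "using a fictional date of exposure that is two months prior to receiving the first vaccine dose". Its purpose is stated as "in order to estimate the influence of variables that are not directly associated with immunological effects of the vaccine". The section names no design, reference time or expected null value for this test.

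Section 9.1 concludes that "the case-control design is likely to be more appropriate as the main analysis", while "SCCS is proposed as a sensitivity analysis for the non-fatal cases". Cases are matched to controls on the date of the TTS event, and vaccination is sought in the 28 days before that date (42 days as sensitivity; Section 9.6.4 gives 42 days).

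In discussing the SCCS, Section 9.1 lists the assumption that "the occurrence of an event of interest must not alter the probability of subsequent exposure" and says it could be violated. It also refers to a possibly high fatality of TTS and to an event delaying vaccination. The stated remedies are a separate period for days -7 to -1 before vaccination and an extended method for curtailed exposure after the event. Both belong to the SCCS.

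Observation generally starts on 02 December 2020. For the SCCS it starts 42 days before the first vaccination in England, and "this results in the date 26th October 2020".

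**The concern.** A falsification test is useful when its expected result without bias is known, normally 1. Here exposure status is fixed by something that happens after the outcome. A person whose TTS is fatal, or whose first dose is put off beyond the window, cannot be fictionally exposed. The matched control has no such event at the index date and is vaccinated on schedule. The outcome therefore helps to determine the exposure. This is the dependence that Section 9.1 recognises for the SCCS, and the fictional date brings it into the case-control design.

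At stake is how the check is read. If the expected OR without bias is below 1, upward bias from behaviour or roll-out can bring the observed value back to about 1, and that would be taken as reassurance. It is the only negative-control analysis that the protocol describes.

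**Working it through.** The protocol gives no figure for this test, so there is none to reproduce. Two months is taken as 61 days; using 60 moves each date and bound by one day.

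**1. Who is fictionally exposed.** Let v be the first-dose date and t the index date. The fictional date is v - 61. Exposure within 28 days before t means v - 61 ≤ t ≤ v - 33, so the real dose falls 33 to 61 days after TTS. With a 42-day window it falls 19 to 61 days after. The SCCS period of days -7 to -1 does not reach either range.

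**2. Expected OR in the case-control design, with no vaccine effect and no bias.** Let p be the chance that a control is vaccinated in that later window, and let s = (1 - fatality) × (1 - deferral) be the share of cases still vaccinated as scheduled. Then

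OR0 = [ps/(1 - ps)] / [p/(1 - p)].

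The values of p, fatality and deferral are assumptions. With p = 0.15, p/(1 - p) = 0.1765.

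| Fatality | Deferral | s | ps/(1 - ps) | OR0 |
|---|---|---|---|---|
| 0 | 0 | 1.00 | 0.1765 | 1.00 |
| 10% | 0 | 0.90 | 0.135/0.865 = 0.1561 | 0.88 |
| 0 | 20% | 0.80 | 0.120/0.880 = 0.1364 | 0.77 |
| 20% | 20% | 0.64 | 0.096/0.904 = 0.1062 | 0.60 |
| 40% | 20% | 0.48 | 0.072/0.928 = 0.0776 | 0.44 |

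The choice of p matters less: at 20% of each, OR0 is 0.63 for p = 0.05 and 0.55 for p = 0.30. A simulation of date-matched sampling with an assumed uniform roll-out agrees. At 20% of each it gives 0.61 with the 28-day window and 0.60 with 42 days.

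**3. Masking.** Multiply a true upward bias of 1.5 by OR0 at p = 0.15:
- s = 0.8: 1.5 × 0.773 = 1.16
- s = 0.7: 1.5 × 0.665 = 1.00
- s = 0.6: 1.5 × 0.560 = 0.84

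**4. Observation start.**
- With the 02 December 2020 start, 02 December + 33 days = 4 January 2021. The 28-day fictional window is wholly unobserved for first doses before about that date.
- 02 December + 61 days = 1 February 2021. The window is partly unobserved for doses up to about that date. By Section 7, AstraZeneca vaccination began in early January, so roughly its first four weeks are affected.
- With the SCCS start, 26 October + 61 days = 26 December 2020, so no AstraZeneca dose is affected.
- Simulated with no fatality and no deferral, the OR is 1.01 with the 02 December start and 1.00 with the 26 October start. The null does not move, because a case and its controls share the index date.

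**5. Dependence on the reference time.** In a simulated SCCS of vaccinated cases with 20% fatality and 20% deferral, the relative incidence is:
- 0.80 with all other time as reference
- 0.90 with all other time as reference and non-fatal cases only
- 1.00 with pre-vaccination time only as reference

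Real post-vaccination time in the reference adds a further problem. If the true relative risk is 3, the fictional estimate falls to about 0.80 (case-control) or 0.77 (SCCS) even with no fatality or deferral.

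**The case against.** The strongest reply is that Section 9.10 fixes no design or reference time, so the expected null is not settled by the text. An SCCS with only pre-vaccination time as reference has a null of 1. This point stands, and a reader who infers that the test's null is always below 1 goes further than the protocol supports. The shift belongs to the case-control form. That form still matters, because Section 9.1 favours it as the main analysis and Section 9.10 states no restriction that would remove the dependence.

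The size is also assumed. The protocol gives no fatality or deferral figure, and its worked example of event-dependent exposure is a second dose withheld, not a first dose. With neither loss the expected OR is 1.00. Vaccination brought forward after an event, or earlier-scheduled doses postponed into the 33 to 61 day band, would push the other way. All of this stands and limits the finding to direction and plausible range.

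It is tempting to count the unobserved early windows as another cause of a null below 1. They are not: date-matched cases and controls lose them equally.

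Nor is it right that the check has no value. With the null below 1, an OR clearly above 1 is still evidence of upward bias, and conservative evidence. Lastly, the analysis is only to be considered, and other bias checks exist, such as censoring before the 07 March 2021 media reports. No primary estimate depends on it.

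**Conclusion.** The point holds for the matched case-control design. The fictional date makes exposure conditional on surviving TTS and being vaccinated about 33 to 61 days later, so deaths, and deferrals that carry the dose past the window, lower the expected OR. For p = 0.15 it falls to 0.88 with 10% fatality, 0.77 with 20% deferral and 0.60 with 20% of each. A true bias of 1.5 would read as about 1.00 if 70% of cases were still vaccinated as scheduled.

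These sizes rest on assumed fatality, deferral and control exposure, and on deferred cases not being vaccinated inside the window. The unobserved early windows are a separate and lesser matter of lost information. What fails is the reading of a value near 1 as absence of bias. The weakness lies in a supporting, optional check, and it should be corrected before that check is used for reassurance.

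**What to change.** Add to Section 9.10 a falsification run that keeps the real vaccination dates and the same matched model but replaces TTS with negative-control outcomes: acute hospital-coded events with no plausible link to vaccination. Exposure then precedes the outcome and the expected OR is 1.

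If the fictional-date run is kept:
- run it in a design whose reference is pre-vaccination time only, for example the SCCS. Its null of 1 assumes that the loss after an event does not depend on how far ahead the dose was due, which should be stated;
- limit it to first doses whose whole fictional window lies inside observation;
- state that a value near 1 from a case-control version is not evidence of no bias.

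The cost is extra outcome code lists in data already linked, some programming, and some lost early doses under the 02 December start. No new data source is needed and the primary analysis does not change.
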